10.0 BIOSTATISTICAL CONSIDERATIONS

10.1 Primary and secondary endpoints

The *primary objective* is to assess the safety and efficacy of inhaled aerosolized cyclosporine A solution in hematopoietic (group A) and lung transplant patients (group B) with bronchiolitis obliterans (BO) or BO syndrome (BOS). The *primary endpoint* of each study group is FEV_1 improvement or stabilization from study baseline at week 18 for two successive measures, at least 1 week apart, no more than two weeks apart.

Criteria for response:

For subjects with progressive disease at study entry, (subjects with a documented decline ($\geq 10\%$) in FEV₁ within 18 weeks of study enrollment), improvement in BO is defined as an FEV₁ increase $\geq 10\%$ compared to baseline and stabilization of BO is defined as less than 10% increase to less than 10% decline in FEV₁ as compared to baseline.

For subjects with stable disease (active BOS, stable by FEV_1 criteria) at study entry (a stable FEV_1 , increase < 5% and decrease < 10% within the 18 weeks preceding study enrollment), improvement in BO is defined as an FEV_1 increase $\ge 10\%$ compared to baseline and stabilization of BO is defined as less than 10% increase to less than 10% decline in FEV_1 with a minimum 25% decrease in the dose of one or more systemic immunosuppressive drugs(assessed at week 18, sustained for 3 weeks, excluding adjustments made for target drug levels) while being treated with CIS. Subjects with stable BO at study entry that have less than a 10% increase to less than a 10% decline in FEV_1 as compared to baseline that have no reduction in systemic immunosuppression while receiving CIS will be considered non-responders. Response will require a confirmatory PFT result at least 1 week after 18 week assessment. The average of these two measurements will be used for assessment of response.

The treatment will be considered successful in each cohort if there is a more than 30% improvement or stabilization. Adverse events associated with the treatment will also be assessed. (Please see the table below)

The secondary objectives of the study are to assess the lung deposition and pharmacokinetics of this CSA preparation, the inflammatory pathways that lead to the development of bronchiolitis obliterans and the anti-inflammatory effects of this CSA preparation ex vivo and in vivo. *Secondary endpoints* will be measured in the laboratory using the results of multiplex cytokine arrays, flow cytometry and gene expression profiling from peripheral blood and bronchoalveolar lavage samples, lung deposition studies and pharmacokinetic studies. Secondary endpoints will also include changes in the six-minute walk tests, high-resolution chest CT images, and quality of life measurements.

We will evaluate response for group A and group B subjects separately, in order to assess if the treatment is effective in each disease.

| Disease at study entry | FEV1 | Systemic | Final Response |
|-------------------------|--------------------|-------------------|----------------|
| | | Immunosuppression | classification |
| Progressive | Improvement (≥10%) | N/A | Improvement |
| $(\geq 10\%$ decline in | | | |
| preceeding 18 wks) | | | |
| Progressive | Stabilization | N/A | Stabilization |
| _ | (<10% increase and | | |
| | decrease <10%) | | |
| Progressive or Stable* | Decline ≥10% | N/A | Non-responder |
| Stable | Improvement (≥10%) | N/A | Improvement |
| (<5% increase and | | | _ |
| decrease <10% in | | | |
| preceeding 18 wks) | | | |

Response Criteria

| Stable | Stabilization (<10% increase and decrease <10%) | Minimum 25% decrease | Stabilization |
|--------|---|-------------------------|---------------|
| Stable | Stabilization (<10% increase and decrease <10%) | N/A | Non-responder |

* Subjects that have decline more than 20% are also non-responders

10.2 Sample size

For each study group, we determine the sample size using the Two-Stage Minimax Design of Simon $(1989)^{20}$. We test the null hypothesis that the proportion of subjects that respond to therapy (improvement or stabilization) is 0.3 or less against the alternative hypothesis that the proportion of subjects that respond to therapy (improvement or stabilization) is 0.5 or more. With alpha = 0.05and 80% power, a maximum of 39 subjects will be needed for each of study groups A and B. In each study group, at the first stage, up to 19 subjects will be accrued and if 6 or fewer subjects have a response to CIS at 18 weeks, we will conclude that the treatment is not effective and we will stop that study group. Note that all 19 subjects may not need to be accrued, as long as 13 subjects do not show improvement or stabilization. If 7 or more of the 19 subjects respond to therapy at 18 weeks at the first stage in one of the study groups, then an additional 20 subjects will be accrued, bringing the total number of subjects to a maximum of 39. If the total number of subjects responding is 16 or fewer, we conclude that the treatment is not effective. If at least 17 of 39 subjects respond we will consider this treatment successful. Once again, this may happen before all 39 subjects are accrued. A 95% confidence interval for the proportion of subjects improving or stabilizing will be given. Based on the sample size of the study, the two-sided confidence interval will be obtained with the binomial exact method or the normal approximation, if appropriate. We will test our null hypothesis (that the proportion of response is 0.3 or less) formally using the confidence interval approach. If the lower 95% limit of the confidence interval is greater than 0.3, we will conclude the null hypothesis is rejected and the study treatment is successful. If the lower 95% limit of the confidence is less than 0.3, we will not reject the null hypothesis.

Subjects who are unable to tolerate a dose escalation to 300 mg but are able to tolerate 150 mg inhalation for at least two weeks will be included in the primary analysis. Subjects who will be considered treatment failures include:

1) those who develop progression of baseline BO (>20% decline in FEV1) during the 18 week course of the study

2) those who are deemed to have progressed at the end of study as evidenced by an FEV1 decline $\geq 10\%$

3) subjects who require increases in existing or addition of new immunosuppressive therapies due to worsening symptoms related to BOS (sustained for 3 weeks, excluding adjustments made for target drug levels) after week 9

4) subjects with BO or BOS who had stable disease (active BOS, stable by FEV_1 criteria) at study entry and are deemed to have a stable FEV_1 , increase < 10% and decrease < 10% at the end of study, with less than a 25% reduction in one or more systemic immunosuppressive medications (sustained for 3 weeks, excluding adjustments made for target drug levels) while receiving CIS. 5) subjects that aren't able to tolerate the 150mg dose for more than two weeks.

All subjects who begin treatment will be included in the primary analysis, except those subjects that are unable to tolerate the 150mg dose for at least two weeks. In order to maintain an adequate sample size, additional subjects will be offered enrollment in order to account for those subjects that were unable to tolerate the 150mg dose for at least two weeks.

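### Three success rules that disagree are given for the primary endpoint, and the one named as the formal test has 72% power, not the stated 80%

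*Combined protocol and SAP*

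**What the plan says.** Section 10.2 of the combined protocol and SAP states that "we determine the sample size using the Two-Stage Minimax Design of Simon". The null is a response proportion of 0.3 or less; the alternative is 0.5 or more. The size claim is "With alpha = 0.05and 80% power, a maximum of 39 subjects will be needed" in each group. Stage 1 stops for futility at 6 or fewer responders of 19. At the end, 16 or fewer of 39 means not effective.

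Three statements then define success:

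- Section 10.1: "The treatment will be considered successful in each cohort if there is a more than 30% improvement or stabilization".
- Section 10.2: "If at least 17 of 39 subjects respond we will consider this treatment successful".
- Section 10.2, a few sentences later, describing the formal test of the null: "If the lower 95% limit of the confidence interval is greater than 0.3, we will conclude the null hypothesis is rejected", in which case the treatment is again called successful. The interval is two-sided, by the exact binomial method or the normal approximation. If the lower limit is below 0.3, the null is not rejected.

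Nothing in sections 10.1 to 10.3 says which statement governs.

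**The concern.** A Simon design for a one-sided null at alpha 0.05 has its decision count built in, here 17 of 39. The lower limit of a two-sided 95% interval is a one-sided test at 0.025, which is stricter, so the two need not agree. The criterion in 10.1 carries neither a sample size nor an error rate.

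At stake is the verdict on the primary endpoint. The trial is single-arm and non-randomised, so the responder count will be known when the verdict is written. An unranked choice of rules could then be settled by the result. The quoted 80% power would also not describe the test that the plan calls formal.

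**Working it through.** **Inputs (section 10.2).** n1 = 19, continue at 7 or more responders; n = 39, so 20 patients in stage 2; p0 = 0.3; p1 = 0.5.

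**Formula.** For success at k or more of 39 after passing stage 1:

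P(success | p) = Σ over x = 7 to 19 of Bin(x; 19, p) × P(Bin(20, p) ≥ k − x).

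**1. The plan's own figure.** With k = 17 this gives 0.0455 at p = 0.3 and 0.8036 at p = 0.5. An exhaustive minimax search with type I error at most 0.05 and power at least 0.80 returns the same design (6/19, 16/39). The sample size of 39 is correct for this rule.

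**2. The count that the interval test needs.**

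Normal approximation, lower limit = p̂ − 1.96 × √(p̂(1 − p̂)/39):
- 17/39: 0.4359 − 1.96 × 0.0794 = 0.280
- 18/39: 0.4615 − 1.96 × 0.0798 = 0.305

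Exact (Clopper-Pearson), lower limit = 2.5% quantile of Beta(x, 39 − x + 1):
- 17/39: Beta(17, 23) gives 0.278
- 18/39: Beta(18, 22) gives 0.301

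Both permitted methods put the threshold at 18.

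**3. Error rates of the three rules, with the stage 1 stop.**

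| Rule | Threshold | Type I error (p = 0.3) | Power (p = 0.5) |
|---|---|---|---|
| Above 30% observed | 12/39 (30.8%) | 28.6% | 91.6% |
| Simon count | 17/39 | 4.55% | 80.4% |
| Lower 95% limit above 0.3 | 18/39 | 2.3% | 72.2% |

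Without the stage 1 stop, the interval rule has power 73.9% and the 30% rule a false-positive rate of 51.8%.

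**4. Verdict by final count.**

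| Responders of 39 | Above 30% | 17 or more | Lower 95% limit |
|---|---|---|---|
| 11 or fewer | fail | fail | fail |
| 12 to 16 | success | fail | fail |
| 17 | success | success | fail |
| 18 or more | success | success | success |

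**5. How often the rules part.** These are differences between success probabilities at adjacent thresholds.
- Exactly 17 at p = 0.5: 0.8036 − 0.7224 = 8.1%. At p = 0.45: 0.5987 − 0.4885 = 11.0%.
- 12 to 16 at p = 0.5: 0.9157 − 0.8036 = 11.2%. At p = 0.45: 0.8236 − 0.5987 = 22.5%.

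**6. Early declaration.** Section 10.2 allows success to be reached before all 39 are accrued. Suppose a group stops at its 17th responder and the interval is computed then. The exact lower limit is 0.304 at 17/36 and 0.295 at 17/37 (normal: 0.309 and 0.299), so the two rules disagree whenever that responder is patient 37, 38 or 39. At p = 0.5 this has probability 12.3%, and the interval rule's power falls to 68.1%.

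**The case against.** The strongest reply is that nothing is miscalculated. The 80% is attached to the Simon design and reproduces; the plan never claims it for the interval. The 72% applies only if the interval sentence governs. That is correct about the sample size. But the interval is what the plan names as its formal test, so a reader is entitled to take it as governing and to expect the stated power from it.

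Second, the criterion in 10.1 may only be shorthand for showing a true rate above the null value of 0.3, with 10.2 supplying the operating rule. That reading is possible. Two rules would then remain, in conflict only at 17 of 39, and the figures for 12 to 16 responders would drop out. As worded, though, the sentence sets a condition for success and contradicts the 16-or-fewer boundary. The 51.8% figure needs the stage 1 stop to be ignored, which the plan does not allow, so 28.6% is the relevant one.

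Third, the interval test is the stricter of the two rules in 10.2, so it does not inflate false positives, and the mismatch looks like a two-sided interval paired with a one-sided design. Both points stand. They explain the conflict but do not resolve it, and the cost falls on power.

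Fourth, the 72.2% and 8.1% assume that accrual runs to 39. So they do; under early declaration the shortfall is larger, not smaller.

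**Conclusion.** The concern holds. At 17 of 39 section 10.2 both declares success and fails to reject its null, under either interval method it permits. If the interval governs, the threshold is 18 of 39, with type I error 2.3% and power 72.2%, about 8 percentage points below the stated 80%. If the Simon count governs, the stated alpha and power are right and the interval sentence is wrong. With the 10.1 criterion taken as written, the range without a single verdict widens to 12 to 17 responders.

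These figures assume the stage 1 stop is applied, 39 evaluable patients, and true rates of 0.3 and 0.5 as in the plan. The conflict at 17 does not depend on how 10.1 is read. This must be fixed before the primary analysis.

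**What to change.** Make 17 or more of 39 the only success rule, and say that the count decides. Replace the two-sided 95% interval test with the lower limit of a two-sided 90% interval, that is, a one-sided 95% bound. It agrees with the count on both sides of the boundary: 0.30001 exact and 0.305 normal at 17/39, against 0.277 and 0.281 at 16/39. The exact margin at 17/39 is very thin, since P(X ≥ 17 | 39, 0.3) = 0.04998, which is why the text should name the count as decisive. The bound also stays above 0.3 if success is declared at the 17th responder before patient 39 (exact 0.309 at 17/38). Keep the two-sided 95% interval as a description of the response rate, and delete the 30% sentence from 10.1.

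If the sponsor prefers the 95% interval test, restate the design as success at 18 or more of 39 and not effective at 17 or fewer, with one-sided type I error 0.023 and power 72%, and tie any early declaration to the 18th responder.

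Either option is a change of wording in 10.1 and 10.2 and needs no additional patients.

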4.0 STUDY DESIGN

The study is designed as a non-randomized, Phase II study of aerosolized cyclosporine A in solution with propylene glycol (CIS) in hematopoietic stem cell transplant recipients at least 99 days post transplant (Group A) or lung transplant recipients at least 6 months post transplant (Group B) who have been diagnosed with biopsy proven bronchiolitis obliterans or Bronchiolitis Obliterans Syndrome. The *primary endpoint* of each study group is FEV₁ improvement or stabilization from study baseline at week 18 for two successive measures, at least 1 week apart, no more than two weeks apart. Subjects who cannot tolerate the medication (at least 150mg dose), have disease progression (beginning at week 9) as defined by a 20% or more decline in FEV₁ on two successive measurements at least 2 weeks apart or require >25% increase in one or more existing immunosuppressive agents or the addition of new systemic immunosuppressive therapies due to worsening symptoms related to BOS will go off study. As of Amendment M, lung transplant patients are no longer being enrolled on this protocol.

* Based on two successive measures at least two weeks apart,

beginning at week 9

11-H-0068 PI: [name]

Version 16 (Amendment N) July 22, 2019

13

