Any subject that demonstrates disease progression (beginning at week 9) as defined by a 20% or more decline in FEV_1 on two successive measurements at least 2 weeks apart, or >25% increase in existing or addition of new immunosuppressive therapies (sustained for 3 weeks, excluding adjustments made for target drug levels), above baseline levels, due to worsening symptoms related to BOS, will be categorized as a treatment failure and will discontinue study drug administration and proceed with end of study drug assessment. For all others, study drug administration will end at week 19 assessment.

Deviation plan for a missed dose: Subjects will be treated with CIS three times weekly ideally on Monday, Wednesday, and Friday of the week. Should a subject miss a scheduled dose of CIS, we will attempt to alter the dosing regimen for that week so that the subject will still receive three doses of CIS over a week with a limit of 1 dose per day. Data will be captured and reported for subjects who deviate from the treatment plan.

Medication Holds: During study participation, subjects may be instructed to hold administration of CIS after development of an adverse event or other reason at the discretion of the PI. Information pertaining to the reason for and the duration of the medication hold will be captured in the subjects' medical record. If study drug is held for more than 7 days, the time of the hold will not be counted towards the overall study week count. Study drug can be held for up to 12 weeks.

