8.1 Pulmonary Function tests

Spirometry measures how much and how quickly air is moved in and out of the lungs. For these tests, the subject breathes into a mouthpiece attached to a recording device (spirometer). The information collected by the spirometer may be printed out on a chart called a spirogram. The more common lung function values measured used to assess the subjects on this trial will include:

Forced vital capacity (FVC). This measures the amount of air you can exhale with force after you inhale as deeply as possible.

Forced expiratory volume (FEV). This measures the amount of air you can exhale with force in one breath. The amount of air you exhale may be measured at 1 second (FEV₁).

Peak expiratory flow (PEF). This measures how quickly you can exhale. It is usually measured at the same time as your forced vital capacity (FVC).

Total lung capacity (TLC). This measures the amount of air in your lungs after you inhale as in your lungs after a normal exhale (FRC) and the amount after you exhale with force (RV).

Maximum voluntary ventilation (MVV). This measures the greatest amount of air you can breathe in and out during one minute.

Exhaled Nitric Oxide. This measures the amount of nitric oxide in your breath after exhalation. This will be performed in a subset of subjects based on the availability of testing staff and scheduling.

Lung Volumes using Nitrogen Washout. This measures the total lung capacity and provides an estimate of residual volume of the lung.

Diffusing Capacity of the lungs for carbon monoxide (DLCO). This measures the ability of the lungs to transfer gas from inhaled air to the red blood cells in pulmonary capillaries.

Peak Flow Measurements: Subjects will be given a home peak flow meter that will measure their peak flow and FEV1. The results will be recorded, and subjects will be given a level below which they should call the research team. Subjects with a decline in peak flow of >20% compared to pretreatment baseline will be instructed to return to the NIH for formal pulmonary function testing and clinical evaluation. Subjects will be encouraged to perform peak flow testing daily, however, failure to perform peak flow measurements will not be considered a protocol deviation.

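### Failure item 1 in section 10.2 (any FEV1 fall above 20% in the 18 weeks) conflicts with the confirmed, week 9 onward progression rule used elsewhere, so a responder with one transient dip can be scored either way

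*Combined protocol and SAP*

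**What the plan says.** Section 4.0 takes subjects off study for "disease progression (beginning at week 9) as defined by a 20% or more decline in FEV₁ on two successive measurements at least 2 weeks apart". Section 6.2.1 repeats the rule and attaches the scoring consequence: such a subject "will be categorized as a treatment failure and will discontinue study drug administration". Section 10.5.2 repeats it again as a reason to stop study drug.

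Section 10.2 lists who counts as a treatment failure. Item 1 is "those who develop progression of baseline BO (>20% decline in FEV1) during the 18 week course of the study". It requires no confirmation, sets no start week, and uses more than 20% where the other sections use 20% or more. Item 2 covers a fall of 10% or more at end of study. Item 3 covers "subjects who require increases in existing or addition of new immunosuppressive therapies due to worsening symptoms related to BOS"; it states that the change must be sustained for 3 weeks and occur after week 9, but omits the >25% threshold given in 6.2.1 and 10.5.2.

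Section 10.1 bases response on the average of the week 18 measurement and its confirmatory repeat. A footnote to its response table adds: "Subjects that have decline more than 20% are also non-responders".

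**The concern.** Sections 6.2.1 and 10.2 both decide who is a failure for the primary endpoint, and they do not give the same answer for every subject. An analyst building the endpoint will work from the 10.2 list. Read literally, it fails a subject for one low spirometry reading at any visit, even if the subject stays on drug and meets the week 18/19 criterion.

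Such readings can occur before week 9. PFTs are scheduled at week 6, and section 8.1 sets no start week when it says: "Subjects with a decline in peak flow of >20% compared to pretreatment baseline will be instructed to return to the NIH for formal".

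The success rule rests on small counts (7 of 19, then 17 of 39), so one subject can decide the outcome. The study is single-arm with no blinding described. If the conflict is left open, the scoring choice could be made with outcomes already in view.

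**Working it through.** **The rules side by side**

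| | 4.0, 6.2.1, 10.5.2 | 10.2 item 1 |
|---|---|---|
| Threshold | 20% or more | more than 20% |
| Window | from week 9 | whole 18 weeks |
| Confirmation | second reading at least 2 weeks later | none stated |

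**A case that separates them.** A subject with progressive disease at entry reads -22% at week 6 or week 12, recovers, and averages -3% at weeks 18/19. Under 6.2.1 there is no confirmed progression, and under 10.1 the result is stabilization, a response. Under item 1 as written the subject is a failure. For a subject stable at entry, the conflict arises only if the 25% immunosuppressant reduction or a 10% FEV1 gain is also met.

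**The footnote in 10.1.** It sits on the row for a decline of 10% or more. At end of study, anyone more than 20% down is already a non-responder on that row, so it adds nothing.

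**The plan's design reproduces.** With stopping at 6 or fewer of 19 and success at 17 or more of 39, the exact binomial calculation is

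P(success | p) = Σ over x = 7 to 19 of P(X1 = x) × P(X2 ≥ 17 - x), where X1 ~ Bin(19, p) and X2 ~ Bin(20, p).

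This gives alpha 0.0455 at p = 0.30 and power 0.8036 at p = 0.50. A full search confirms it as the minimax design with N = 39. The chance of stopping at stage 1 when p = 0.50 is 0.084.

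**How many subjects are affected.** The documents give no SD, visit correlation or true change for FEV1, so all three are assumed. The simulation used 2,000,000 subjects per setting and PFTs at weeks 6, 9, 12, 15, 18 and 19, with normal percent changes from baseline and equal correlation between visits.
- Correlation: 1/3, 0.5 or 0.7. The value 1/3 comes from a shared baseline that averages two readings (section 2.4) with equal independent errors: covariance 0.5σ² over variance 1.5σ².
- Literal rule: any reading below -20% at weeks 6 to 15.
- Confirmed rule: both readings at or below -20% at weeks 9/12, 12/15 or 15/18.
- Counted: literal rule met, confirmed rule not met, and week 18/19 average above -10%.

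Share of all subjects, at correlation 1/3 / 0.5 / 0.7:

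| SD (points) | No true change | True change -5% |
|---|---|---|
| 5 | at most 0.2% | at most 0.2% |
| 7 | 0.6 / 0.3 / 0.1% | 2.6 / 1.4 / 0.3% |
| 10 (upper bound) | 4.9 / 3.1 / 1.2% | 9.2 / 5.6 / 2.1% |

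The taper condition for stable subjects was then applied, assuming half are progressive at entry and half of stable subjects are tapered. The SD 7 rows become 0.4 / 0.3 / 0.1% and 2.0 / 1.0 / 0.2%. Varying both fractions from 25% to 75% moves the largest SD 7 case between 1.1% and 2.4%. Unscheduled PFTs triggered by peak flow are not modelled.

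**Effect on the design.** Let d be the share of responders failed only by the literal rule. At SD 7, d runs from 0.1% to 3.2% and hardly changes with the taper condition. The response rate becomes p × (1 - d). In the worst SD 7 case, 0.50 × (1 - 0.032) = 0.484 and 0.30 × (1 - 0.032) = 0.290.

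| SD 7 | Power at 0.50 (correlation 1/3 / 0.5 / 0.7) |
|---|---|
| Confirmed rule | 0.804 |
| Literal, no true change | 0.794 / 0.798 / 0.802 |
| Literal, true change -5% | 0.746 / 0.774 / 0.797 |

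In the worst SD 7 case the stage 1 stop at 0.50 rises from 0.084 to 0.107, and alpha falls from 0.045 to 0.034.

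**When one subject decides.** At a true rate of 0.50, stage 1 ends on exactly 7 of 19 with probability 9.6%. The trial passes stage 1 and ends on exactly 17 of 39 with probability 8.1%. In either case, reclassifying one responder reverses the decision under the count rule.

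**The case against.** The strongest reply is that item 1 is shorthand. It uses the word progression, which the protocol defines three times in the same way, and item 3 of the same list also abbreviates. Read so, item 1 has a clear job. Section 10.5.2 lets subjects taken off drug for progression continue assessments, so the off-study rule in 10.3 would not automatically make them non-responders; item 1 would. The reply adds that the effect is tiny: at SD 7 with no true change, at most 0.6% of subjects (0.006 × 39, about 0.2 of a subject). The 0.746 power figure needs the lowest correlation and an assumed 5% mean decline. Subjects whose only dip is at week 6 are 0.02 to 0.6% at SD 7. The literal reading also cannot produce a false efficacy claim.

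The points on size and direction stand. The shorthand reading is plausible and may be what was meant, but the text does not establish it. Item 1 gives its own threshold and its own window, and that window contradicts a week 9 start. Item 3 writes out its timing and persistence, so their absence from item 1 cannot safely be read as implied. Sections 10.1 to 10.3 do not say which rule prevails.

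**Conclusion.** The concern holds. The primary-endpoint failure rule in 10.2 conflicts with the progression rule in 4.0, 6.2.1 and 10.5.2 on confirmation and start week, and slightly on threshold. The classification of a subject with a transient dip is not fixed in advance.

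The expected effect is small: below 3% of subjects at SD 5 or 7, and up to 9.2% only at SD 10, which is an upper bound with no support in the documents. These figures rest on the assumed SD, correlation and true change. The literal reading can only remove responders, so it may cost power and slightly raise the chance of a futility stop, but it does not inflate type I error. The power loss applies only if 0.50 was set for the confirmed rule; if 0.50 is the rate for the endpoint as listed in 10.2, power is unchanged. The sample size of 39 per group is not in error. The point is worth correcting because it concerns the primary endpoint and the remedy is almost free.

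**What to change.** Reword 10.2 item 1 to state the rule in 6.2.1: an FEV1 fall of at least 20% from baseline, counted from week 9 and confirmed on the next successive measurement two or more weeks later, with a cross-reference to 6.2.1. Leave item 2 (end-of-study decline of 10% or more) unchanged. Either cross-reference the 10.1 table footnote to the same rule or delete it.

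The cost is one sentence in 10.2 and one cross-reference in 10.1. No data, visits or sample size change, and the design keeps alpha 0.0455 and power 0.804.
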